5.9.2. Other Composite Outcomes

The other objectives include triple endpoint (HbA1c $< 7\%$ and no weight gain [$< 0.1\text{ kg}$] at Week 28, and no documented symptomatic hypoglycemia [BG $< 3.9\text{ mmol/L}$] during the maintenance

period); double endpoint (HbA1c <7% at Week 28 and no documented symptomatic hypoglycemia [BG < 3.9 mmol/L] during the maintenance period), and double endpoint (HbA1c <7% and with no weight gain [<0.1 kg] at Week 28) will be analyzed by the same model as that in Section [5.8.15.7.1](#).

5.10. Efficacy Analysis without Censoring Post-Rescue or Early-Discontinuation Data

We will conduct some additional efficacy analysis without censoring the data after rescue therapy or premature treatment discontinuation (whichever occurs first). Missing endpoints will be imputed by jumping to the reference (J2R) method as described in Carpenter et al. 13, which assumed that the drug effect for missing data in both the placebo arm and dulaglutide arm was like the observed effect in the placebo arm. This approach in essence assumed that subjects would lose any treatment effect after the intercurrent events, which might be used as a worst-case scenario in terms of assuming patients with missing data received no drug benefit after the intercurrent events. Measurements include actual and change from baseline in HbA1c, body weight and FSG and frequency counts and percentage of patients achieving the target of HbA1c <7.0%. We will analyze HbA1c, body weight and FSG by ANCOVA model. For HbA1c, treatment and OAM usage are fixed effects and baseline is a covariate. For body weight and FSG, treatment, OAM usage, baseline HbA1c strata (<8.5%, and ≥8.5%) are fixed effects, and baseline dependent variable is a covariate. Percentages of patients achieving the target of HbA1c <7.0% will be analyzed using logistic regression with treatment and OAM usage as fixed effects and baseline HbA1c value as a covariate.

5.11. Safety Analyses

The safety analysis will include analysis of adverse events (AEs), hypoglycemic and hyperglycemic episodes, vital signs, and laboratory analytes. Unless otherwise specified, the ITT population will be used for analyses of safety measures.

5.11.1. Adverse Events

An AE is any untoward medical event associated with the use of a drug in humans, whether or not it is considered related to a drug. Adverse events will be coded from the actual term described by the investigator using the Medical Dictionary for Regulatory Activities (MedDRA). Unless otherwise specified, AEs will be reported using the MedDRA system organ class (SOC) and preferred term (PT). Selected AEs may be reported using MedDRA high-level terms (HLT).

The following SMQs will be used to identify CV events:

1. Ischaemic heart disease SMQ
 - a. Myocardial infarction SMQ (20000047)
 - b. Other ischaemic heart disease SMQ (20000168)
2. Central nervous system haemorrhages and cerebrovascular conditions SMQ

- a. Conditions associated with central nervous system haemorrhages and cerebrovascular accidents SMQ (20000166)
- b. Haemorrhagic central nervous system vascular conditions SMQ (20000064)
- c. Ischaemic central nervous system vascular conditions SMQ (20000063)

3. Cardiac failure SMQ (20000004)

The following Standardized MedDRA Queries (SMQs) and customized Lilly Search Categories (LSC) will be used to identify Acute Pancreatitis (SMQ) and Chronic Pancreatitis (LSC):

- Acute Pancreatitis SMQ
 - Apply the Acute Pancreatitis SMQ (20000022), narrow terms only
- Chronic Pancreatitis LSC
 - Search for following PTs
 1. Pancreatitis chronic (10033649)
 2. Pancreatic duct obstruction (10052765)
 3. Pancreatic failure (10079281)
 4. Pancreatic enlargement (10055024)
 5. Pancreatic duct dilatation (10064858)
 6. Sphincter of Oddi dysfunction (10066424)
 7. Ampulla of Vater stenosis (10067376)
 8. Pancreatic calcification (10068823)

The following LSC will be used to identify Thyroid Neoplasm:

1. Thyroid neoplasms (10043747)
2. Thyroid neoplasms malignant (10043749)
3. Thyroid disorders NEC (10043712)
 - a. 2 PTs only: Thyroid C-cell hyperplasia (10070568) and hypercalcitoninaemia (10072001)

The following SMQs will be used to identify Allergic and Hypersensitivity Reactions:

- Apply the following SMQs, narrow terms only
 - 1. Hypersensitivity SMQ (20000214)
 - 2. Anaphylactic Reaction SMQ (20000021)
 - 3. Angioedema SMQ (20000024)

The following LSC will be used to identify Injection Site Reactions:

- Find PTs nested within the HLT of Injection Site Reactions (10022097). Separately look at the following terms (a subset from the list above) which are potentially immune-mediated injection site reactions:
 1. Injection site dermatitis
 2. Injection site erosion
 3. Injection site erythema

4. Injection site hypersensitivity
5. Injection site induration
6. Injection site pruritus
7. Injection site exfoliation
8. Injection site vasculitis
9. Injection site photosensitivity reaction
10. Injection site rash
11. Injection site urticaria
12. Injection site hypertrophy
13. Injection site inflammation
14. Injection site irritation
15. Injection site oedema
16. Injection site warmth

For hepatic safety, apply the Drug related hepatic disorders - comprehensive search SMQ (20000006).

All AEs and treatment-emergent adverse events (TEAEs), defined as an event that first occurs or worsens (increases in severity) on or after first dose will be listed by patient and visit using MedDRA PT and SOC. Information on treatment, preferred term, reported term, severity, seriousness, and relationship to study drug will be reported. Listings of patients with study and study drug discontinuation due to AEs or death will be produced.

Summary statistics will be provided for TEAEs, SAEs, and study and study drug discontinuation due to AEs or death during the treatment period and through safety follow-up. Counts and proportions of patients experiencing AEs will be reported for each treatment group, and Fisher's exact tests will be used to compare the treatment groups.

Listings and summary statistics will also be provided for adverse event of special interest (AESI) including deaths, hypoglycemia, severe, persistent hyperglycemia, nonfatal CV events, adjudicated and confirmed pancreatitis, thyroid neoplasm, allergic and hypersensitivity reactions.

Since gastrointestinal (GI) AEs, like diarrhea, nausea, abdominal distension and vomiting, are among the most common events reported in patients treated with dulaglutide, summaries and analyses for onset, duration, and severity of diarrhea, nausea, abdominal distension and vomiting will be provided. The duration of an adverse event was calculated as adverse event end date minus the adverse event start date plus 1 day and was reported in terms of median number of days. Time to onset of an adverse event was analyzed by day, from the first dose date of the study drug to the occurrence of the adverse event.

The following PTs will be used to identify GIAEs:

1. Specific diarrhea symptoms include the following PTs
 - a. Diarrhea (10012735)
 - b. Fecal volume increased (10049939)

- c. Frequent bowel movements (10017367)
- 2. Specific nausea symptoms include the following PTs
 - a. Retching (10038776)
 - b. Procedural nausea (10066962)
 - c. Nausea (10028813)
- 3. Special abdominal distension symptoms include the following PTs
 - a. All PTs nested within the HLT of flatulence, bloating and distension (10016770)
- 4. Specific vomiting symptoms include the following PTs
 - a. Retching (10038776)
 - b. Vomiting (10047700)
 - c. Vomiting projectile (10047708)

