9.2.2.4. C-Cell Hyperplasia and C-Cell Neoplasms

Individuals with personal or family history of certain thyroid or nonthyroid endocrine abnormalities or certain preexisting laboratory and genetic characteristics will be excluded from the study (see Section 6.2). Patients with a personal or family history of MTC or personal history of MEN 2 syndrome, or who have serum calcitonin $\geq 20 \text{ pg/mL}$ at study entry as determined by the central laboratory will be excluded. The assessment of thyroid safety during the trial will include reporting of thyroid treatment-emergent adverse events (TEAEs) and measurements of calcitonin according to the Schedule of Activities (Section 2). The purpose of calcitonin measurements is to assess the potential of dulaglutide to affect thyroid C-cell function, which may indicate development of C-cell hyperplasia and neoplasms.

Patients who develop serum calcitonin increases $\geq 50\%$ of the screening value AND an absolute value $\geq 20 \text{ pg/mL}$ and $< 35 \text{ pg/mL}$ at Visit 17 (Week 28) will be asked to repeat the measurement within 1 month. If this repeat value is increasing ($\geq 10\%$ increase), the patient will be encouraged to undergo additional endocrine assessment and longer-term follow-up by an endocrinologist to exclude a serious adverse effect on the gland.

Patients with an increase in serum calcitonin $\geq 50\%$ of screening value AND an absolute value ≥ 35 pg/mL at Visit 17 (Week 28) will be recommended to immediately undergo additional endocrine assessments and longer term follow-up by an endocrinologist.

For patients who require additional endocrine assessment because of increased calcitonin concentration per criteria provided in this section, data from the follow-up assessment will be collected in the specific section of the eCRF.

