Sitting BP and PR will be measured using standardized equipment provided by the Sponsor according to the Schedule of Activities (Section 2). Vital sign measurements should be taken before obtaining an ECG tracing and before collection of blood samples for laboratory testing, at visits where required (see Schedule of Activities Section 2). The patient should be allowed to sit quietly for 5 minutes before vital sign measurements. An appropriately sized cuff (cuff bladder encircling at least 80% of the arm) should be used to ensure the accuracy of BP measurements. The arm used for the BP measurement should be supported at heart level. At Visit 1 (screening), to determine which arm should be used to collect BP and PR throughout the study. BP and PR will be measured once in each arm and the arm that had the higher BP should be used to collect all 2 measurements of both BP and PR at all study visits. For each parameter (PR, SBP/diastolic blood pressure [DBP]), 2 measurements will be taken using the same arm; the recordings should

be taken at least 1 minute apart. Each measurement of sitting PR and BP is to be recorded in the eCRF. Any AE related to changes in BP and PR should be reported.

9.4.3. *Laboratory Tests*

For each patient, laboratory tests detailed in ([Appendix 2](#)) should be conducted according to the Schedule of Activities (Section [2](#)).

Any clinically significant findings from laboratory tests that result in a diagnosis and that occur after the patient receives the first dose of investigational product(s) should be reported to Lilly or its designee as an AE via eCRF.

9.4.4. *Body Weight, Height, and Body Mass Index*

Body weight will be measured at prespecified time points (see Schedule of Activities, Section [2](#)). Each patient's weight should be measured according to a standardized protocol. Body mass index will be computed from the patient's weight and height.

9.4.5. *Safety Monitoring*

Lilly will periodically review evolving aggregate safety data within the study by appropriate methods.

Specific safety measures are included in the protocol to ensure appropriate monitoring of pancreatic (Section [9.2.2.3](#)), thyroid (Section [9.2.2.4](#)), and liver safety (Section [9.4.5.1](#)).

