
Safety:
 
 • To compare the addition of dulaglutide 1.5 mg QW with the addition of placebo QW to titrated basal insulin glargine for selected safety parameters through 32 weeks in patients with T2D (unless noted otherwise). 	
 • Incidence of TEAEs, SAEs and discontinuation of study drug due to AEs. • Change from baseline in electrocardiograms, laboratory and vital sign measurements. • Incidence of AESI. • The incidence of deaths and nonfatal CV events. • Occurrence of hypoglycemic episodes. • Incidence of patients initiating rescue therapies due to severe, persistent hyperglycemia. • Incidence of adjudicated and confirmed pancreatitis. • Incidence of thyroid neoplasm. • Incidence of allergic and hypersensitivity AEs.

Exploratory
 
Efficacy:
 
 • To compare the addition of dulaglutide 1.5 mg QW with the addition of placebo QW to titrated basal insulin glargine for exploratory efficacy parameters after 28 weeks of treatment in patients with T2D. 	
 • Frequency of insulin dose adjustments through 28 weeks. • Number of insulin dose assessments per TTT algorithm and compliance with the TTT algorithm at Week 6, 8, and 12. • Proportion of patients achieving HbA1c target of <7.0%, and without weight gain (<0.1 kg) at Week 28, and without documented symptomatic hypoglycemia (BG <3.9 mmol/L) during the maintenance period (Weeks 12-28). • Proportion of patients achieving HbA1c target <7.0% and without weight gain (<0.1 kg) at Week 28; • Proportion of patients achieving HbA1c target of <7.0% at Week 28, and without documented symptomatic hypoglycemia (BG <3.9 mmol/L) during the maintenance period.

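### SAP 5.11.1 counts AEs coded to C-cell hyperplasia or hypercalcitoninaemia as thyroid neoplasm: the wide search is defensible, but the reported row is mislabelled

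*SAP*

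**What the plan says.** Protocol Section 4 and SAP Table 4.1 both list the safety endpoint "Incidence of thyroid neoplasm".

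The SAP makes it operational in 5.11.1, where "The following LSC will be used to identify Thyroid Neoplasm" introduces a three-item list (LSC is a sponsor-defined search category). Items 1 and 2 are the groups for thyroid neoplasms and malignant thyroid neoplasms. Item 3 goes to a different group, thyroid disorders not elsewhere classified, and takes from it "2 PTs only: Thyroid C-cell hyperplasia (10070568) and hypercalcitoninaemia (10072001".

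The same section promises listings and summary statistics for a set of events of special interest that includes "adjudicated and confirmed pancreatitis, thyroid neoplasm, allergic and hypersensitivity reactions". Preferred terms arise by coding: "Adverse events will be coded from the actual term described by the investigator using the Medical Dictionary for Regulatory Activities (MedDRA".

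Protocol 9.2.2.4, headed with both C-cell hyperplasia and C-cell neoplasms, explains the calcitonin testing: "The purpose of calcitonin measurements is to assess the potential of dulaglutide to affect thyroid C-cell function". It treats a change in that function as a possible pointer to either condition. Under Protocol 9.4.3, a post-dose laboratory result is to be reported as an adverse event when it belongs to "Any clinically significant findings from laboratory tests that result in a diagnosis".

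**The concern.** The name of the endpoint is narrower than what is counted under it. Someone reading the summary table would take a case of thyroid neoplasm to be a tumour. The list also admits C-cell hyperplasia and raised blood calcitonin, and neither document says the endpoint is meant to include them. The protocol keeps the ideas apart: 9.2.2.4 names hyperplasia and neoplasms as two things that calcitonin may point to, and the discontinuation criteria in 8.1.1 name C-cell hyperplasia alongside medullary thyroid carcinoma rather than as a form of it.

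What is at stake is how one rare safety count is read. A finding about C-cell function and a finding of a tumour call for different conclusions, and a single summary row cannot show which one has been observed.

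**Working it through.** The documents state no thyroid event rate, so there is no planned figure to reproduce. The check is to follow a case through the text and then see how much one case could move the row.

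**Route into the count**

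1. The endpoint is the incidence of thyroid neoplasm (Protocol Section 4; SAP Table 4.1).
2. A case is any adverse event whose preferred term is on the list in SAP 5.11.1. No narrower rule is given elsewhere.
3. The two added terms are on that list. They had to be drawn from a third, non-neoplasm group, so the SAP's own structure shows that they are not among its neoplasm terms.
4. No later step removes them. Pancreatitis is summarised as adjudicated and confirmed, while thyroid neoplasm carries no such qualifier (SAP 5.11.1).
5. No row separates them. For injection site reactions, the same section takes a broad group and then asks for a subset to be examined on its own. The thyroid list has no such instruction.

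Hence a patient whose only thyroid event is coded to hypercalcitoninaemia or to C-cell hyperplasia is counted as a thyroid neoplasm.

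**Which test results could start this route**

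- Calcitonin is scheduled at Visits 1 and 3 and again at Visit 17 or early termination (Protocol Section 2).
- Visit 1 precedes treatment, and a value of 20 pg/mL or more there is exclusionary (criterion 24). The Visit 3 sample is due before study drug is taken. Treatment-emergent events start at the first dose (SAP 5.11.1). These two visits cannot realistically contribute treatment-emergent cases.
- That leaves Visit 17 or early termination. An event reported after that test still counts, because summaries run through safety follow-up (SAP 5.11.1).
- The number itself goes to the laboratory analysis (SAP 5.11.6). It reaches the neoplasm row only if the investigator reports an adverse event and that event is coded to a listed term.

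**Size**

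The planned arm is 145 patients (SAP 5.1); the ITT denominator may be slightly smaller. Assume 0 to 2 true neoplasms in the trial.

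| Non-tumour AEs in one arm | Share of arm |
|---|---|
| 1 | 1/145 = 0.69% |
| 2 | 2/145 = 1.38% |

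One extra event turns 0 cases into 1, raises 1 case by 1/1 = 100%, or raises 2 cases by 1/2 = 50%.

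Fisher's exact test, the SAP's method for comparing adverse event proportions:

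- 1/145 v 0/145: the single event falls in either arm with probability 0.5, so the two-sided p = 0.5 + 0.5 = 1.0.
- 2/145 v 0/145: the probability that both fall in a given arm is (145 × 144)/(290 × 289) = 20,880/83,810 = 0.249, so the two-sided p = 2 × 0.249 = 0.50.

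**The case against.** The strongest reply is that the list fits the protocol. Protocol 10.3.4.2 says that summaries will cover the events of special interest defined in 9.2.2, and the only thyroid entry there is headed with C-cell hyperplasia as well as neoplasms. Picking exactly two terms from a broad group looks deliberate, and a wide safety search errs towards over-reporting. This stands: the search is defensible and should be kept. It does not justify the label, because the endpoint in both documents says neoplasm and nothing more.

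A second reply is traceability. SAP 5.11.1 lists every adverse event by patient with its preferred term, so with one or two events a reader can see what each one was. This also stands and limits the harm, but the summarised incidence still carries the wrong name.

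A reader might go further and infer that any raised calcitonin result is counted as a thyroid neoplasm. The documents do not support that. A value counts only through an investigator-reported, coded adverse event, and Protocol 9.4.3 asks for one only where a clinically significant result leads to a diagnosis. Protocol 9.2.2.4 sends raised Week 28 values to a repeat test or endocrine assessment, with follow-up data in a dedicated form section; it does not tell sites to record an adverse event.

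**Conclusion.** The point holds as a minor one. As written, SAP 5.11.1 would report an adverse event coded to C-cell hyperplasia or hypercalcitoninaemia as a case of thyroid neoplasm. The effect is confined to the label and count of one descriptive safety endpoint. Efficacy results, alpha and sample size are unaffected.

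The percentages rest on an assumed handful of events and on full planned arms; the documents support neither a particular event rate nor a prediction that such an adverse event will occur. A reader might also infer that one or two such events would decide the comparison between arms. The p-values of 1.0 and 0.50 show that they would not.

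**What to change.** In SAP 5.11.1:

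- Keep the full search and report it as a combined row labelled *thyroid neoplasm, C-cell hyperplasia or hypercalcitoninaemia*.
- Derive the endpoint, incidence of thyroid neoplasm, from list items 1 and 2 only.
- Show thyroid C-cell hyperplasia and hypercalcitoninaemia each on its own row.

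This retains the wide net that Protocol 9.2.2.4 implies and makes the neoplasm figure mean what its name says. It needs SAP wording and no new data. The downside is one or two extra table rows with few events.

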5.11.2. Hypoglycemic Episodes

Level 1, 2, 3, and nocturnal hypoglycemia will be included for summary and analysis.

Classification of these hypoglycemic events are shown in [Table 5.2](#).

Table 5.2 Definitions of Hypoglycemic Event Categories

Glycemic criteria/description	
Level 1 (Glucose Alert Value)	Blood Glucose <70 mg/dL (3.9 mmol/L) and >= 54 mg/dL (3.0 mmol/L)
Level 2 (Clinically Significant Hypoglycemia)	Glucose <54 mg/dL (3.0 mmol/L)
Level 3 (Severe Hypoglycemia)	A severe event characterized by altered mental and/or physical status requiring assistance for recovery (no specific glucose threshold).

Nocturnal hypoglycemia: a hypoglycemia event (including severe hypoglycemia) that occurs between bedtime and waking.

A listing of the individual hypoglycemic episodes will be presented using all randomized population. Summary reports will include both incidence and rates of hypoglycemia for each visit including safety follow-up, as well as in stabilization period (Week 0 – 4), maintenance period (Week 12 – 28) and overall period (Week 0 – 28) will be reported for the ITT population without post-rescue or early-discontinuation data.

The incidence of hypoglycemic episodes will be summarized by frequencies and proportion for each treatment group using ITT population, by visit, stabilization period, maintenance period as well as overall period. The overall frequency and proportion are calculated as the total number of patients and proportion of patients reporting hypoglycemic episodes through safety follow-up. The maintenance frequency and proportion are calculated as the total number of patients and

proportion of patients reporting hypoglycemic episodes during Weeks 12 to 28. Treatment differences in the incidence of hypoglycemic episodes will be assessed using Fisher's exact test.

The rates of hypoglycemic episodes (episodes/patient/year) for each visit, overall and maintenance period will be analyzed using a generalized linear mixed-effects model assuming negative binomial distribution. The model will include treatment, OAM usage (metformin alone, acarbose alone, metformin and acarbose), baseline HbA1c strata (<8.5% vs. $\geq 8.5\%$), as fixed effects. The logarithm of days between visits will be included as an offset to account for possible unequal duration between visits and between patients.

Three additional categories of hypoglycemia will be used in efficacy analysis in Section 5.8.1 and 5.9.2. The definitions are below:

Total hypoglycemia: all level 1/2/3 events combined.

Documented symptomatic hypoglycemia with BG <3.0 mmol/L (or 3.9 mmol/L): any time a patient felt that s/he was experiencing symptoms and/or signs associated with hypoglycemia and had a BG <3.0 mmol/L (or 3.9 mmol/L).

Asymptomatic Hypoglycemia: an event not accompanied by typical symptoms of hypoglycemia, but with a measured BG <3.9 mmol/L.

